### **Primary/Secondary Outcomes**

Outcomes at 12 months will be analysed using a generalised linear model which will adjust for minimisation and baseline covariates. The development of treatment effects over time will be explored using repeated measures mixed effects models that make use of available outcome data at each time point, e.g. 6, 12 and 24 months for the POP-SS (this assumes outcome data missing at random conditional on the observed covariates).

Furthermore, it is anticipated that many women may be asymptomatic one year after surgery and their POP-SS will be zero. A composite binary/linear model will be used to analyse the primary outcome (POP-SS at 12 months) so that a distribution of POP-SS with a high proportion of zero values is taken into account. The binary element will be based on a POP-SS=0, and the linear element will treat the POP-SS score as a continuous measure with possible values ranging from 0 to 28.

The menu design of the trials will be taken into account in the analyses of all outcomes. Both RCTs have 3 strata, as shown in Table 2 and Table 3.

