6.3 Statistical analysis

A single principal analysis is anticipated at 12 months after the last woman is recruited. The Data Monitoring Committee will determine the frequency of confidential interim analyses, but at present these are planned on four occasions during the data collection period.

All analyses within the RCT will be based on the intention-to-treat principle. All outcomes in both trials will be described with the appropriate descriptive statistics where relevant: mean and standard deviation for continuous and count outcomes, or medians and inter-quartile range if required for skewed data, numbers and

percentages for dichotomous and categorical outcomes (for example subjective recurrence of prolapse).

Analysis of the primary outcome (POP-SS) will estimate the mean differences (and 95% confidence interval) between the intervention and control groups using a general linear model that adjusts for the minimisation covariates and other important prognostic covariates, including the baseline symptom score, at 12 months after surgery. A similar analysis will be used to analyse the primary outcome at 6 and 24 months.

All secondary analyses will be analysed in a similar manner but using the appropriate generalised linear model (for example logistic regression for dichotomous data such as subjective prolapse failure, Poisson or negative binomial regression for count data such as number of nights in hospital) or time to event methods (e.g. Cox regression on time to further surgery) where required. We will explore analysing outcomes at all time points simultaneously using for example, Generalised Estimating Equations or Generalised Linear Latent and Mixed Models, and relevant link functions, to explore changes in outcome over time.

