## Sample Size and Power Calculation

In an average population of women having prolapse surgery, about 70% will be having a primary procedure. Two comparisons will be made:

- a standard repair versus a standard repair using a biological graft inlay; and
- a standard repair versus a standard repair using a non-absorbable or combined mesh inlay.

Pilot data have shown that a conservative estimate of the standard deviation of the primary patient-reported outcome POP-SS is 8 units. A difference in means of 2 units would represent an improvement in the response to a POP-SS question, for example, a feeling of something coming down or in the vagina, from 'Most of the Time' to 'Occasionally'. To detect a standardised difference of 0.25 with 90% power and alpha equal to 0.025 (to maintain the nominal p value at 0.05 with two tests being used), we would need to randomise 400 women to each arm of the study. Best efforts using evidence based techniques will be employed to maximise the response rate at follow up. Nevertheless, we feel it prudent to inflate the estimated sample size for 15% dropout at one year requiring approximately 1450 women having primary surgery to be recruited to the trial. Adjusting for baseline covariates and minimising the loss to follow up will potentially improve this power. A trial of this size would also be adequately powered to detect important differences in the economic and secondary outcomes.

It is estimated that the other 30% of women requiring anterior and/or posterior repair will receive a secondary or subsequent repair. Therefore, during the proposed time period required for recruiting 1450 women to the primary repair RCT above, it is anticipated approximately 620 women having secondary surgery will be eligible and will be willing to be randomised. Within the secondary RCT two comparisons will be made:

- a standard repair versus a standard repair using a non-absorbable or combined mesh inlay; and

- a standard repair versus a mesh kit procedure.

It would be possible to detect with 90% power and alpha equal to 0.025 a standardised effect size of 0.38 which equates to 3 points on the POP-SS scale (this estimated effect detectable has been calculated adjusting for potential 15% dropout at one year). The pilot data from IMPRESS indicated that women having secondary repairs have a higher level of symptoms at baseline. Therefore it is biologically plausible that these women may show a larger benefit from the options available.

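### The SAP names two analyses of the primary outcome without ranking them, and leaves the composite model's linear part and the combination of its parts undefined

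*SAP*

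**What the plan says.** Protocol 6.3 fixes the effect measure: "Analysis of the primary outcome (POP-SS) will estimate the mean differences (and 95% confidence interval) between the intervention and control groups", from a general linear model with covariate adjustment.

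The SAP agrees at first. General Methods promises mean differences with 95% confidence intervals for continuous outcomes, tested at the 5% level. Primary/Secondary Outcomes opens with a generalised linear model for 12-month outcomes, adjusted for the minimisation factors and baseline covariates.

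The same section then expects many women to score zero and says: "A composite binary/linear model will be used to analyse the primary outcome (POP-SS at 12 months". The binary part is a score of zero or not. In the other part, "the linear element will treat the POP-SS score as a continuous measure with possible values ranging from 0 to 28". The SAP gives no ranking of the two models, no statement of who enters the linear part, and no rule for combining the parts. Its Sensitivity analyses section deals with missing data only and does not mention the composite model.

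The sizing rests on one quantity: "A difference in means of 2 units would represent an improvement in the response to a POP-SS question". The SAP sets the calculation out as: "To detect a standardised difference of 0.25 with 90% power and alpha equal to 0.025".

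**The concern.** A trial sized on a single mean difference should say that this mean difference decides the question. Here a second model is assigned to the same outcome, and it can return two more results: an odds ratio for zero and a linear coefficient. With no ranking, the choice among them could be made after the results are seen, although Protocol 2.6 promises predefined analyses.

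The undefined linear part raises a further problem. The usual two-part model fits its continuous part to women with scores above zero. That group is formed by the outcome of surgery, so randomisation does not protect the comparison. An operation that clears mild symptoms leaves a more severe group above zero and can look harmful there while being better overall.

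A related detail is that the SAP (Primary Outcomes) scores missing items as zero, which can add women to the zero group and so affects the binary part.

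**Working it through.** **1. The plan's own figure.** The inputs are in SAP, Sample Size and Power Calculation: difference 2, SD 8 ("a conservative estimate of the standard deviation of the primary patient-reported outcome POP-SS is 8 units"), power 90%, and alpha 0.025 per comparison ("to maintain the nominal p value at 0.05 with two tests being used"). Sidedness is not stated.

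n per arm = 2 × (z₀.₉₈₇₅ + z₀.₉₀)² × SD² / difference² = 2 × (2.2414 + 1.2816)² × 64 / 4 = 397.2, so 398.

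The SAP says "we would need to randomise 400 women to each arm of the study", which gives 90.2% power. A one-sided 0.025 gives 337 and does not reproduce the figure, so two-sided is inferred. The sized quantity is the difference in means over all women.

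**2. Linear part on all women, as written (0 to 28).** Its coefficient is the ordinary mean difference, and step 1 applies unchanged. What is added is the odds ratio for zero: a second test of the same outcome with no rank.

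**3. Linear part on scores above zero only.** Use E[Y] = P(Y>0) × E[Y | Y>0]. The documents give no zero share, so assume 10% to 40% in the control arm and a true overall difference of 2 points.

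| Control zeros | Difference above zero, equal zero shares: 2 / (1 − share) | Difference above zero, effect wholly in extra zeros |
|---|---|---|
| 10% | 2.22 | 0 |
| 20% | 2.50 | 0 |
| 30% | 2.86 | 0 |
| 40% | 3.33 | 0 |

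The sign can also reverse. In a constructed example, scores of 0, 4 and 12 occur in 20%, 50% and 30% of controls and in 70%, 0% and 30% of treated women.
- Overall means: 0.5 × 4 + 0.3 × 12 = 5.6, against 0.3 × 12 = 3.6. Treatment is 2 points better.
- Means above zero: 5.6 / 0.8 = 7.0, against 3.6 / 0.3 = 12.0. Treatment looks 5 points worse.

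A simulation used 400 per arm, alpha 0.025 and skewed scores with nominal mean 9 above zero, rounded and capped at 28. Rounding and capping brought the realised overall difference to 1.8-2.0. Rejection rates across 10-40% control zeros were:
- above-zero test, effect all in the zeros: about 3%, in effect no power;
- above-zero test, effect split: 48% to 80%;
- above-zero test, effect all above zero: 98% to 100%;
- all-women mean difference, every case: 94% to 99%.

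**4. Recombination.** Forming P(Y>0) × E[Y | Y>0] in each arm and subtracting returns the overall mean difference exactly (1.71 and 1.71 on a simulated data set).

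**5. False-positive rate for one pooled comparison.** SAP Table 2 gives 253 + 178 = 431 women on standard repair and 256 + 181 = 437 on synthetic mesh. With 15% loss these become 366 and 371. The level is 5%, from General Methods.
- With no true effect, the zero/non-zero test and the above-zero test are close to independent: 1 − 0.95² = 9.75%.
- Simulation with 10-20% zeros: all-women mean difference alone, about 5%; mean difference or zero/non-zero, about 9%; any of the three, about 11%.
- A second assumed distribution (19% zeros, mean 5.6) gave about 10% and 12% for the last two.

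The range is therefore about 9-12%. Raising the zero share to 40% hardly moves it.

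**The case against.** The case for the plan is strong in several respects.

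- The composite paragraph is worded as an addition, and the adjusted model comes first. A reader might infer that the SAP has abandoned the mean difference. The documents do not support that: it remains in Protocol 6.3, in SAP General Methods and in the opening of Primary/Secondary Outcomes.
- A reader might infer that using zeros in both parts biases the result. It does not. On the literal wording the linear part is the sized mean difference, and a jointly fitted zero-inflated or censored model can properly use zeros in both parts.
- A two-part model is a recognised choice for a score with many zeros, and step 4 shows it can return the target.
- The sign reversal is constructed, and every zero share here is assumed.
- The SAP does not say that any significant component would count as success.
- A reader might count every test of the primary RCT (both comparisons, RCT1 alone and pooled, three tests each: 12 in all) and reach about 30%. That figure does not belong to this point. Four linear tests with no composite model already give about 14.5%. Only the rise within one comparison is due to the composite model.

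All of this stands. What it does not supply is a ranking, a population for the linear part, or a combination rule. The composite model is also assigned directly to the primary outcome and is not listed as a sensitivity analysis.

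**Conclusion.** The point holds in a limited form. The sized mean difference is estimated, and the sizing reproduces (398 against 400 per arm). The defect is that two analyses of one primary outcome are unranked and the second is incompletely defined.

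Its size depends on the reading. With zeros in the linear part, the cost is an unranked second test. With zeros out, the coefficient is not the sized quantity: for a true 2-point benefit it can run from 2.2-3.3 points through zero to the wrong sign. If any significant component were taken as success, the error rate for one pooled comparison would rise from about 5% to about 9-12%. These figures rest on assumed zero shares and score shapes, and the last also on 15% loss and that rule for declaring success. The absence of a ranking and of a definition rests on the text alone. The change should be made because it removes a choice that could otherwise follow the data.

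**What to change.** In SAP Primary/Secondary Outcomes, state that for each randomised comparison the single primary analysis is the covariate-adjusted mean difference in POP-SS at 12 months over all randomised women. Robust standard errors are an option for the spike at zero, not a requirement.

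Label the composite model supportive. Define its continuous part on scores 1 to 28, recombine the two parts into one marginal mean difference with a bootstrap interval, and say that the above-zero part alone will not be read as a treatment effect.

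The cost is a few sentences of SAP text and a little extra analysis. It needs no new data and changes no sample-size figure.

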**Table 2: Number of participants randomised to each stratum in the primary RCT**

Stratum	Standard repair (A)	Synthetic mesh (B)	Biological mesh (C)
RCT1	253	256	255
RCT1B	178	181	n/a
RCT1C	116	n/a	114

**Table 3: Number of participants randomised to each stratum in the secondary RCT**

Stratum	Standard repair (A)	Synthetic mesh (B)	Mesh kit (C)
RCT2	24	24	44
RCT2B	31	28	n/a
RCT2D	1	n/a	3

In the primary RCT, RCT1 will be analysed on its own and treatment effects for treatments B and C (compared with A) will be estimated. In addition, the RCT1 and RCT1B strata will be combined (using just data in arms A and B) in a separate model to create a further estimate of the treatment effect between A and B. Similarly, the RCT1 and RCT1C strata will be combined (using just data in arms A and C) in a separate model to create a further estimate of the treatment effect between A and C. Where strata are combined, the stratum variable will be fitted as a fixed effect in the model. The secondary trial will be similarly analysed, although RCT2 will not be combined with RCT2D due to the small number randomised to RCT2D.

Secondary outcomes will be analysed in a similar fashion to the primary outcome using appropriate link functions.

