## **Statistical Methods**

### **General Methods**

The statistical analysis of the RCTs will be based on all women as randomised, irrespective of subsequent compliance with the treatment allocated (intention to treat). The principal comparisons will be:

- In women having a primary prolapse repair,
  - a standard anterior and/or posterior repair will be compared with a standard repair using a biological graft inlay; and
  - a standard anterior and/or posterior repair will be compared with a standard repair using a non-absorbable or combined mesh inlay.
- In women having a secondary prolapse repair,
  - a standard anterior and/or posterior repair will be compared with a standard repair using a non-absorbable or combined mesh inlay; and
  - a standard anterior and/or posterior repair will be compared with a mesh kit procedure using an introducer device.

The two trials are being considered independently because different surgical options are considered to be appropriate for clinical reasons. Women who are not randomised but who are in the Comprehensive Cohort group will be analysed according to the operation actually carried out.

Descriptive statistics will be tabulated by treatment allocation for all outcomes (mean and SD for continuous data, proportions for binary data). Treatment effects will be estimated with 95% confidence intervals for all outcomes (mean differences for continuous data, odds ratios for binary data). Statistical significance will be at the 5% level and corresponding confidence intervals will be derived. Analyses will be conducted using SAS v9.3.

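### For three of the four principal comparisons the SAP plans two estimates, three-arm stratum alone and strata combined, and does not say which is primary.

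*SAP*

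**What the plan says.** SAP, Primary/Secondary Outcomes, explains how the menu design is handled. Women in the primary RCT were randomised in three strata, counted in SAP Table 2 ("Number of participants randomised to each stratum in the primary RCT"):

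| Stratum | Standard (A) | Synthetic mesh (B) | Biological mesh (C) |
|---|---|---|---|
| RCT1 | 253 | 256 | 255 |
| RCT1B | 178 | 181 | – |
| RCT1C | 116 | – | 114 |

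The text under Table 3 gives two analyses of the same contrasts. In the one listed first, "RCT1 will be analysed on its own and treatment effects for treatments B and C (compared with A) will be estimated". In the other, RCT1 and RCT1B are pooled "in a separate model to create a further estimate of the treatment effect between A and B", and RCT1 and RCT1C are pooled likewise for A v C, with stratum as a fixed effect. Secondary outcomes follow the same pattern. So does the secondary trial, except that RCT2 is not pooled with RCT2D, so mesh kit v standard has one estimate only.

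No sentence in the SAP or the protocol ranks the two estimates. Under General Methods, the SAP says that the analysis "will be based on all women as randomised, irrespective of subsequent compliance".

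**The concern.** Two models estimate one effect and test one hypothesis, and the plan has no rule for the case where they differ. The order of the text puts the three-arm stratum first. The commitments to take the menu design into account and to analyse women as randomised point towards the combined model. A reader cannot tell which estimate answers the principal question, although protocol section 2.6 promises that all analyses will be predefined.

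Two things are at stake. If the estimate listed first is taken as the main result, women validly randomised to the same comparison in another stratum do not contribute, and much of the recruited power is lost. If the choice stays open until results are known, the error rate for each comparison is no longer the one in the design.

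**Working it through.** **Inputs.** From SAP, Sample Size and Power Calculation: "A difference in means of 2 units would represent an improvement in the response to a POP-SS question"; "a conservative estimate of the standard deviation of the primary patient-reported outcome POP-SS is 8 units"; "To detect a standardised difference of 0.25 with 90% power and alpha equal to 0.025"; 15% dropout at one year. Arm sizes are from SAP Tables 2 and 3. SAP General Methods gives a different level: "Statistical significance will be at the 5% level and corresponding confidence intervals will be derived". Both levels are used below.

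**The plan's own figure.** n per arm = 2(z₁₋α/₂ + z₁₋β)²/δ², with δ = 2/8 = 0.25. At two-sided α = 0.025 and 90% power this is 2 × (2.2414 + 1.2816)²/0.0625 = 397.2, so 398 against the stated 400. Two-sided 0.05 gives 337, so the design figure is a two-sided 0.025 calculation.

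**Women left out by RCT1 alone.**
- A v B: 178 + 181 = 359 of 253 + 256 + 359 = 868, or 41%.
- A v C: 116 + 114 = 230 of 253 + 255 + 230 = 738, or 31%.

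**Power.** Each stratum carries information I = ab/(a + b), summed over strata when stratum is a fixed effect. Power = Φ(0.25√(0.85·I) − z), with z = 2.2414 at α 0.025 and 1.9600 at α 0.05.
- A v B: RCT1 127.2; RCT1B 89.7; sum 217.0.
- A v C: RCT1 127.0; RCT1C 57.5; sum 184.5.

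| Comparison | Analysis | 0.25√(0.85·I) | Power, α 0.025 | Power, α 0.05 |
|---|---|---|---|---|
| A v B | RCT1 alone | 2.600 | 64.0% | 73.9% |
| A v B | RCT1 + RCT1B | 3.395 | 87.6% | 92.4% |
| A v C | RCT1 alone | 2.597 | 63.9% | 73.8% |
| A v C | RCT1 + RCT1C | 3.131 | 81.3% | 87.9% |

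With no dropout and α 0.025, RCT1 alone has 72% for each comparison, and combined strata have 93% and 88%. With SD 7 (the value in protocol Appendix IV), 15% dropout and α 0.025, the figures are 77% alone, and 95% and 91% combined.

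**How often the two differ.** RCT1 is nested in the combined data, so the two test statistics have correlation √(I_RCT1/I_sum): √(127.2/217.0) = 0.77 for A v B and √(127.0/184.5) = 0.83 for A v C. From the bivariate normal distribution, with a true 2-point effect, α 0.025 and 15% dropout:
- A v B: only the combined estimate significant 24.8%, only RCT1 significant 1.3%, total 26.1%.
- A v C: 19.3% and 1.9%, total 21.2%.

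**Error if either may count.** With no true effect, the chance that at least one estimate is significant is 4.1% (A v B) or 3.9% (A v C) at nominal 2.5%, and about 8% for each at nominal 5%.

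**Secondary trial, standard v inlay.** For the 3-point difference in the SAP, δ = 3/8. RCT2 alone (24 v 24) has I = 12.0. Adding RCT2B (31 v 28, I = 14.7) gives 26.7. With 15% dropout and α 0.025, power is 15% alone and 32% combined.

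**The case against.** Much can be said for the SAP. Both analyses are prespecified and stratum is handled properly. The commitment to take the menu design into account, and a sample size of 400 per arm that only the combined strata come near (431 v 437 and 369 v 369), suggest that the combined model is meant to be principal. The disagreement is mostly one of precision: the estimates are strongly correlated, and RCT1 alone is rarely the only significant one. The 4% error rate arises only if either estimate may be used to claim success, which the documents do not propose. The power figures ignore covariate adjustment, which the SAP plans and which would raise all of them; the documents give no correlation from which to quantify this.

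These arguments limit the point but do not remove it. A principal analysis that has to be inferred from hints is not named, and the words that introduce the combined models as additional point the other way.

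Some stronger readings are tempting and are not supported:
- That all four principal comparisons are affected. Mesh kit v standard has a single estimate.
- That each comparison loses 44% of its women. That figure is 589/1353, the share of the whole primary RCT outside RCT1. RCT1B has no arm C and RCT1C has no arm B, so the relevant losses are 41% and 31%.
- That the RCT1 analysis breaches intention to treat. The sentence on women as randomised mainly concerns compliance, and within RCT1 women stay in their allocated arms.
- That interim results could have steered the choice. Protocol section 8.4.1 keeps them confidential to the DMC and those who supply the analyses, and nothing says that those people choose the estimate.

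**Conclusion.** The point stands for A v B and A v C in the primary RCT and for standard v mesh inlay in the secondary RCT: two unranked estimates of one effect, for the primary and the secondary outcomes.

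The cost of relying on the three-arm stratum is a fall in power from 88% to 64% (A v B) and from 81% to 64% (A v C). This assumes 2 points, SD 8, two-sided α 0.025, 15% dropout, a simple comparison of means and no covariate gain. At the 5% level in General Methods the falls are from 92% and 88% to 74%. The gap remains under every dropout and SD variant tried.

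It would go too far to say that the trial has no defined result. The likely outcome is a narrower and a wider interval around similar values. But in a fifth to a quarter of trials with a true 2-point effect the two would fall on different sides of the significance threshold, and the plan does not say which then answers the question.

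**What to change.** Before the 12-month analysis, state in the SAP that for all outcomes the primary estimate is the combined-strata model with stratum as a fixed effect:
- RCT1 + RCT1B for standard v synthetic mesh inlay (primary RCT);
- RCT1 + RCT1C for standard v biological graft (primary RCT);
- RCT2 + RCT2B for standard v mesh inlay (secondary RCT).

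Label the RCT1-alone and RCT2-alone estimates of these three comparisons as sensitivity analyses, reported with intervals and carrying no test. Mesh kit v standard keeps its single RCT2 estimate.

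The combined model compares women only within strata in which both options were open to them, so randomisation is preserved and every woman randomised between the two options in the pooled strata is used. The cost is a sentence or two of SAP text; both sets of models are already planned.

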APPENDIX IV LONG TERM FOLLOW-UP

Background

PROSPECT (PROlapse Surgery, Pragmatic Evaluation by randomised Controlled Trial) is the largest randomised controlled trial conducted to date of the use of mesh in women having prolapse surgery. It addresses the use of no mesh, a biological mesh inlay, and a nonabsorbable mesh inserted as an inlay or used in a kit; and separately in women having their first prolapse operation or repeat surgery.

PROSPECT recruited 3091 women from 35 centres across the UK between January 2010 and August 2013. There were two trials, one amongst women having their first prolapse operation (Primary trial, where 1353 women were randomised to no mesh, non-absorbable mesh inlay or biological mesh inlay); and those having repeat surgery (Secondary trial, where 155 women were randomised to no mesh, non-absorbable mesh inlay or mesh kit). Women who were not eligible for randomisation were enrolled into the Comprehensive Cohort (1583 women). The following information was collected:

- Demographic and surgical information at recruitment and at operation;
- Patient reported outcome data (prolapse symptoms, urinary, bowel and sexual function and EQ-5D) through questionnaires at 6, 12 and 24 months;
- Randomised women were examined 12 months after surgery to identify treatment success and adverse effects;
- Information about complications, readmissions, reoperations and costs.

Within the main PROSPECT trial short term failure (within two years of the prolapse operation) was captured. However, as prolapse is a progressive and relapsing condition, with surgery having a high failure rate¹ (repeat surgery occurs on average 12 years later) it is essential to capture the long term failure in order to truly evaluate the potential benefits of mesh versus its adverse effects, which may also occur many years later.² In addition, there is very little information about the long term effects of this condition on urinary, bowel and sexual function,

Current evidence

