## Study Design

PROSPECT is a multi-centred randomised control trial with a parallel-cohort design. The aim of the study is to investigate the safety, effectiveness and cost-effectiveness of operations for women with pelvic organ prolapse. The study includes two RCTs within a Comprehensive Cohort Study, with the following principle objectives:

In women having a primary prolapse repair, the effects of a standard repair versus the following:

- 1) Standard repair using a biological graft inlay
- 2) Standard repair using a non-absorbable or combined mesh inlay

In women having a secondary prolapse repair, the effects of a standard repair versus the following:

- 3) Standard repair using a non-absorbable or combined mesh inlay
- 4) Mesh kit procedure

Treatment allocation is minimised by age (>60/60+), type of planned prolapse surgery (anterior/posterior/both), concomitant continence procedure and concomitant prolapse procedure. Treatment allocations are summarised in Figure 1.

[figure not shown]

Figure 1. Treatment allocation in PROSPECT RCTs

Since recruitment began, additional randomisation menu options have been made available, partly as a result of some mesh types being unavailable on

certain days. It is possible in RCT1 to randomise just between standard repair and non-absorbable mesh (RCT1B), or between standard repair and biological mesh (RCT1C). In the secondary trial, an additional menu option of randomising between standard repair and mesh kit has been added (RCT2D).

At close of recruitment (August 2013), there were 36 participating centres throughout the UK. The centres are listed in Table 1.

**Table 11**– PROSPECT participating centres

Aberdeen	Cumbria	Maidstone	Rotherham
Ayrshire & Arran	Derby	Manchester	South Devon
Barnsley	Exeter	Mid Yorkshire	South Tees (Friarage)
Birmingham	Harrogate	Middlesex	South Tees (James Cook)
Bolton	Huddersfield	North Devon	Sunderland
Bradford	Hull	Nottingham	Taunton
Brighton	Imperial	Plymouth	Whipps Cross
Bristol	Leicester	Portsmouth	Wolverhampton
Chester	Luton & Dunstable	Preston	York

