## **Secondary Outcomes**

### *General*

- immediate and late post-operative morbidity (injury to organs, excess blood loss, blood transfusion, infection (UTI, sepsis, abscess), pain, urinary retention, constipation)
- other adverse effects or complications including mesh erosion or removal
- operating time
- blood loss
- number of nights in hospital
- time until resumption of usual activities

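### The SAP's adjusted odds-ratio model has no fallback for rare harms in the secondary trial, where about three events would face eight parameters

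*SAP*

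**What the plan says.** The SAP (Primary/Secondary Outcomes) states: "Outcomes at 12 months will be analysed using a generalised linear model which will adjust for minimisation and baseline covariates". Its General Methods section promises treatment effects with 95% confidence intervals for all outcomes, as "odds ratios for binary data". After Table 3 it adds: "Secondary outcomes will be analysed in a similar fashion to the primary outcome using appropriate link functions". Protocol 6.3 names logistic regression for dichotomous outcomes.

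The outcomes covered include organ injury, transfusion, sepsis and abscess, and "other adverse effects or complications including mesh erosion or removal" (SAP, Secondary Outcomes, General).

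The adjustment set follows from the SAP's Study Design section: "Treatment allocation is minimised by age (>60/60+), type of planned prolapse surgery (anterior/posterior/both), concomitant continence procedure and concomitant prolapse procedure". Where strata are pooled, stratum is added as a fixed effect.

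On size, protocol Appendix IV reports the "Secondary trial, where 155 women were randomised to no mesh, non-absorbable mesh inlay or mesh kit". The SAP's one concession to small numbers is that "RCT2 will not be combined with RCT2D due to the small number randomised to RCT2D". Neither document sets a minimum event count, a reduced covariate set, an exact or penalised method, or a descriptive-only rule for sparse outcomes.

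**The concern.** Logistic regression by maximum likelihood needs events spread across the levels of every term. When all events, or none, fall in one level of a factor (separation), the likelihood keeps rising as that coefficient goes to infinity and no finite estimate exists. With a handful of events and eight parameters this is the expected result, not an unlucky one.

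Safety is part of the principal objective in protocol 1.2, and uncertainty about mesh harms is a main reason for the trial. If the prescribed model fails on those outcomes, the analyst must choose a replacement after seeing the data. Protocol 2.6 says analyses will be predefined to avoid exactly that.

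**Working it through.** **Check of the plan's own figure.** SAP Table 3 sums to 24 + 24 + 44 + 31 + 28 + 1 + 3 = 155, which matches protocol Appendix IV. The documents give no probability of model failure to reproduce.

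**Models actually planned.**
- Standard v inlay, RCT2 + RCT2B: (24 + 31) v (24 + 28) = 55 v 52, or 107 women.
- Standard v kit: RCT2 only, since RCT2D is not pooled. The SAP analyses the three-arm primary stratum on its own, estimating both contrasts, and treats the secondary trial likewise. The model therefore holds 24 + 24 + 44 = 92 women, with 24 v 44 in the kit contrast.

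**Parameters.** Minimisation factors: age 1, prolapse type 2, continence procedure 1, upper vaginal procedure 1, total 5.
- Pooled model: intercept 1 + treatment 1 + stratum 1 + 5 = 8.
- RCT2 model: intercept 1 + treatment 2 + 5 = 8.

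**Event risks.** Protocol Appendix I gives 2.8% organ damage with introducer devices (section 1.3), and mesh erosion of 6% with biological and 10% with non-absorbable mesh (section 1.2.2). Expected events at 2.8%: 107 × 0.028 = 3.0 and 92 × 0.028 = 2.6.

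**Simulation.** Covariate shares come from the protocol: both compartments 30%, continence procedure 15%, upper vaginal procedure 30%, and the anterior:posterior split of the remainder from the national operation counts. Assumptions: age 60 or over in 50%, independent covariates, the same risk in every arm. Separation was detected by linear programming, for any term and then for the treatment term alone.

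| Risk in every arm | Expected events (107 / 92) | No finite full-model fit (107 / 92) | Treatment odds ratio non-finite (inlay / kit) |
|---|---|---|---|
| 2.8% | 3.0 / 2.6 | 93% / 96% | 45% / 66% |
| 5% | 5.4 / 4.6 | 72% / 86% | 15% / 39% |
| 10% | 10.7 / 9.2 | 30% / 44% | 1% / 7% |

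**Exact cross-check of the last column.** The treatment odds ratio is certainly non-finite if either arm has no events. With arm sizes a and b that probability is 1 − [1 − (1−p)^a][1 − (1−p)^b].
- p = 2.8%, 55 v 52: 0.972^55 = 0.210 and 0.972^52 = 0.228, so 1 − 0.790 × 0.772 = 39%.
- p = 2.8%, 24 v 44: 0.972^24 = 0.506 and 0.972^44 = 0.287, so 1 − 0.494 × 0.713 = 65%.
- The same formula gives 12% and 37% at 5%, 7% and 28% at 6%, and 0.7% and 8.9% at 10%.

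These are floors. The simulated 7% for the kit at 10% lies slightly below its floor through sampling error, so 7–9% is the fair reading.

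**Mesh erosion.** With no standard-arm events the odds ratio is infinite. At an assumed 1% (standard) v 10% (mesh):
- Inlay: 0.99^55 = 0.575 and 0.9^52 = 0.004, so 1 − 0.425 × 0.996 = 58%.
- Kit: 0.99^24 = 0.786 and 0.9^44 = 0.010, so 1 − 0.214 × 0.990 = 79% (about 78% by simulation).

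**Sensitivity.** With age shares of 30% or 70%, full-model failure at 2.8% stays at 93–96%; with 15% loss to follow-up it is 95–97%. Dropping all minimisation covariates still leaves failure in some term in 53% (107 women) and 82% (92 women) at 2.8%, so a shorter covariate list alone is not a cure.

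**Primary trial.** Failure is 3–6% at 2.8% and about zero at 5% or more. It reaches 44–57% only at 1%.

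**The case against.** The strongest objection is that full-model failure is not failure of the treatment estimate. If only the continence-procedure term separates, the treatment odds ratio stays finite. This stands: a reader might infer from 93% and 96% that the harm comparison is nearly always lost, but the treatment-specific figures are 45% and 66% at 2.8% and fall quickly as risk rises.

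A reader might also infer that an erosion odds ratio against standard repair can never be finite. The documents do not support that. Analysis is by intention to treat, and protocol 2.3 lets the surgeon choose the method for a concomitant de novo repair outside the allocation. A woman allocated standard repair may therefore carry mesh, and an event in that arm is unlikely rather than impossible.

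Nor does the point extend to every binary outcome in the secondary trial: at 20% risk, full-model failure is 8% or less. Bias in the finite estimates was not calculated and is not claimed.

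It can also be said that the SAP's wording is loose. It asks only for a similar approach with suitable links, its covariate sentence concerns 12-month outcomes, and its baseline covariates are unlisted. The protocol refers to dummy tabulations that are not available here, and proportions by arm will be tabulated anyway. That softens the rule but supplies no alternative. A change of link does not remove separation, and General Methods still requires an odds ratio with an interval for every binary outcome.

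Finally, three events tell little under any estimator. That is true, but it argues for saying in advance what will be reported.

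**Conclusion.** The concern holds for rare harms in the secondary trial. At 2.8% risk the prescribed model would have no finite solution in more than nine trials in ten, and the treatment odds ratio would be non-finite in roughly 45% (inlay) and 66% (kit). By 10% in every arm the treatment figures are about 1% and 7–9%. Mesh erosion is the exception at that rate, because events will be concentrated in the mesh arms: at 1% v 10% the odds ratio is non-finite in about 58–78%.

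The figures rest on an assumed age split, independent covariates and equal risk across arms, except for erosion. Event risks other than 2.8%, 6% and 10% are assumptions, as is applying the introducer-device rate of 2.8% to every arm. Surgeon is left out: protocol 2.3 lists it as a minimisation factor and the SAP does not. Ten surgeons as fixed effects (an assumed number) would raise full-model failure to 99–100% at risks of 2.8–10%. The primary analysis is untouched. This should be corrected, but it does not threaten the trial's main conclusion.

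**What to change.** Add a sparse-event rule after the SAP sentence on secondary outcomes.

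- **Trigger:** for example, fewer than 10 events in total in the comparison, or an arm with no events. Ten events correspond to 10/107 = 9.3% in the inlay comparison and 10/68 = 14.7% in the kit contrast. In RCT1 + RCT1B (253 + 256 + 178 + 181 = 868 women) they correspond to 1.2%, so the primary trial is rarely affected. A trigger of 10 events per parameter would be far too wide: with 8 parameters it means 80 events, which would remove adjustment from nearly every binary outcome in the secondary trial.
- **Below the trigger:** Firth-penalised logistic regression with treatment and, where pooled, stratum only, plus the risk difference with a score interval.
- **Mesh exposure or removal:** the risk in each arm with an exact interval, and no odds ratio when the standard arm has no events.
- **Above the trigger:** the planned adjusted model. State what is done if a covariate term still separates; the same fallback would serve.

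The cost is a short paragraph and the FIRTH option in PROC LOGISTIC of SAS, the package the SAP already names. The downside is no covariate adjustment for outcomes that meet the trigger.
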